### Research Questions and Hypotheses:

*Specific Aim 1: To determine the impact of service dogs and determine who benefits the most.*

**Hypothesis 1A:** Individuals partnered with SDs will have greater improved mental health over time (Primary outcome will be the PCL checklist. Secondary mental health will be quantified by scores on depression and alcohol use).

**Hypothesis 1B:** Individuals partnered with SDs will have improvements over time in secondary factors of physical, psychosocial, and socioeconomic variables. The secondary factors are defined as follows: 1) physical factors: co-morbidities, medication use, sleep 2) psychosocial factors: community participation, quality of life and 3) socioeconomic factors: demographic and health care utilization and out-of-pocket health care expenses.

*Specific Aim 2: To determine costs associated with total health care utilization and mental health care utilization among Veterans with mental health disorders needs and service or therapy dogs.*

**Hypotheses 2A:** Individuals partnered with SDs will have decreased mental health care utilization over time.

**Hypotheses 2B:** Individuals partnered with SDs will have decreased total health care utilization over time.

*Specific Aim 3: To determine recommendations for providing service dogs to Veterans.*

Develop a strategic plan to provide service dogs to Veterans. A consensus meeting will be planned and will include all investigators of the project along with key individuals from funding agency to discuss findings of study.

*Secondary Aim:* To compare study findings to another VA funded study that is providing dogs as pets to Veterans with PTSD. Both studies are using similar measures to assess mental and psychosocial factors. Data will be compared across groups (SD to dog as a pet) to determine if the highly trained dogs help the Veteran more than having a dog as a pet.

*Projected Time Table*

Training of SDs is time intensive and expensive, with limited numbers of dogs who actually graduate. We will work with vendors to obtain the dogs, but recognize that there may be a significant waiting period prior to pairing. To demonstrate maximum treatment benefits, the data collection phase of this three-year study will be conducted for a minimum 18 months (maximum of 24 months for early enrollees) as we feel the acclimation period for the human-animal bond is longer than 18 months. This allows sufficient time for statistical analyses.

*Timeline*

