TASK	YEAR 1				YEAR 2				YEAR 3				YEAR 4				YEAR 5			
	Apr 2011	June 2011	Aug 2011	Oct 2011	Jan 2012	Apr 2012	Aug 2012	Oct 2012	Jan 2013	Apr 2013	Aug 2013	Oct 2013	Jan 2014	Apr 2014	Aug 2014	Oct 2014	Jan 2015	Apr 2015	Aug 2015	Oct 2015
Start up activities, finalize data collection forms, hire and train data collectors	Shaded																			
Renewal training for data collection				Shaded			Shaded													
Advertisement/promotion of study	Shaded	Shaded	Shaded	Shaded																
Recruit participants, collect baseline	Shaded	Shaded	Shaded	Shaded	Shaded															
STUDY HOLD**					Blue	Blue	Blue	Blue	Blue	Blue										
Collect 3-, 6-,9-, 12- 18- and 24-month data on enrolled veterans			Shaded	Shaded	Shaded	Shaded	Shaded	Shaded	Shaded	Shaded	Shaded	Shaded	Shaded	Shaded	Shaded	Shaded	Shaded	Shaded	Shaded	Shaded
Enter data in electronic database and conduct on-going verification			Shaded	Shaded	Shaded	Shaded	Shaded	Shaded	Shaded	Shaded	Shaded	Shaded	Shaded	Shaded	Shaded	Shaded	Shaded	Shaded	Shaded	Shaded
Conduct statistical analyses and summarize findings																				
Apply for additional funding to support follow up work																				
Dissemination of Findings																				
Prepare manuscripts																				Shaded

\*\* Because of ongoing vendor issues, enrollment was stopped for a second time and new vendors have been awarded contracts. Study will extend beyond the three year period utilizing Veterans who signed consent prior to second hold.

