### **Research Design and Methods**

#### *Design*

This 3-year, mixed methods modified, non-randomized trial will follow individuals for two years. Due to the inability to recruit veterans interested in participating in a control (no dog) group, this group has been eliminated going forward with the study. The study will examine the influence of SDs by assessing the longitudinal change in mental health assessment over time among veterans who have PTSD. The group will consist of individuals partnered with SDs. Following initial screening for inclusion criteria, including criteria set by dog vendors, subjects who are eligible will receive a SD. This study will measure changes over time in the primary outcome of mental health. Additional outcomes in psychosocial health and healthcare utilization will be included. Recruits successfully completing the screening process will be placed on a vendor's waiting list to receive a SD upon the dog's completion of training. Recruits who do not meet all criteria, including vendor criteria, will be ineligible to participate..

Data will be collected at baseline and at 3, 6, 9, 12, 18 and 24 months for individuals with service dogs. For those awaiting service dogs, repeated assessments will occur every 3 months until obtaining a SD. Once baseline data has been collected for 24 months, assessments will occur every 6 months until the Veteran is paired with a SD. Baseline data will include detailed information on the characteristics of the participants, their mental health, psychosocial well-being, socioeconomic and healthcare utilization characteristics. As we want to obtain information regarding the changes in health and wellbeing over time, a prospective study will permit this type of comparison.

*Sample:* The study will use a convenience sample of VHA patients who are currently in treatment for PTSD. We have chosen to use these criteria as a safety measure for the veteran and the dogs. At this time, there are currently 600 veterans receiving care at James A. Haley VAMC for PTSD, with an estimated 25 new veterans seen in the clinic per week. We are confident that an adequate number of Veterans will be recruited for the study. We will monitor recruitment and retention numbers on a monthly basis. The use of additional VA hospitals as a potential source for recruitment is the contingency plan should we be unable to meet enrollment numbers.

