We will be enrolling up to 220 Veterans to be paired with service dogs. The previously cited longitudinal study had only an eight percent attrition rate. Although similar methods are included in this proposal, we recognize that this is a different population; we will plan on a higher attrition rate. Thus, we are estimating a 15 percent drop-out rate ( $n=33$ ), and we will over-recruit participants. Up to two hundred and twenty participants will be recruited over the course of the study. These recruitment numbers are chosen with the expectation that *200 individuals* will complete the study.

A repeated measures design with one fixed effects (any one covariate [TBD]) and 1 within subject effect (time; each subject is measured 5 times [minimum]) achieves approximately 100% power to test the primary fixed effect (dog group status) if a Geisser-Greenhouse Corrected F Test is used with an alpha level=5% and the actual effect  $SD=0.47$  (effect size=5.54). Further, this design achieves approximately 100% power to detect a significant effects among both covariates (alpha level=5%,  $SD=0.8$ ; effect size=5.54) and significant interaction between both the primary fixed effect (dog group status) and each of the covariates (alpha level=5%,  $SD=0.8$ ; effect size=5.54). This analysis assumes a 1st order auto correlation between repeated assessments equal to 0.80.

To assure that we recruit sufficient sample size, we will initiate the following strategies: (1) carefully consider respondent burden when finalizing the baseline survey and interview schedule, (2) employ and train research assistants/data collectors with previous experience in collecting data and who have good communication skills, (3) provide a small reimbursement (\$10.00) for participant time and effort each time a questionnaire is returned, (4) develop posters and recruitment flyers which will be displayed in all mental health clinical areas, and (5) provide in-services on a regular basis to the PTSD and other mental health clinicians explaining the study. These methods have been used successfully in the past by the research team.

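### The stated power is for a dog-versus-control effect that the planned enrolment no longer supplies; none is stated for the within-group PCL change that remains

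*Combined protocol and SAP*

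**What the plan says.** All references are to the combined protocol and SAP.

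- **Objective.** Hypothesis 1A: "Primary outcome will be the PCL checklist". Design section: "This study will measure changes over time in the primary outcome of mental health".
- **Groups.** The Design section says that, because Veterans could not be recruited to a "control (no dog) group, this group has been eliminated going forward with the study". It adds: "The group will consist of individuals partnered with SDs". The Sample section agrees: "We will be enrolling up to 220 Veterans to be paired with service dogs".
- **First power statement (Sample).** The design "achieves approximately 100% power to test the primary fixed effect (dog group status", using a Geisser-Greenhouse corrected F test at 5%, with an effect SD of 0.47, an effect size of 5.54 and a first-order autocorrelation of 0.80. Similar power is claimed for covariates and for a "significant interaction between both the primary fixed effect (dog group status) and each of the covariates". Time is named as the within-subject effect, but no power is given for it.
- **Second power statement (Power analysis for Hypotheses 1).** With at least 65 per group, power exceeds 80% for differences in socioeconomic characteristics. It is said to rest on published PCL-C means and SDs, but no values are given.
- **Analysis.** The Hypothesis 1A model is described as testing change over time between groups. The Hypothesis 1B text and the exploratory analysis that follows it define group as service dog versus control.
- **Numbers.** The Sample section expects 15% dropout (33) from 220 and 200 completers. The Timeline footnote says: "Study will extend beyond the three year period utilizing Veterans who signed consent prior to second hold". The waiting-period text under Screening Visit withdraws Veterans still unpaired at 48 months.

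**The concern.** The sample size is justified by power for a comparison that the current design does not set up. The comparison that the design does set up, PCL over time in Veterans with dogs, has no stated power, no target change and no PCL SD. A reader or the monitoring board could take the figure of about 100% as applying to the analysis that will be run. A confidence interval at the end would still show which changes are excluded, but nobody could say what change the study was sized to detect. The primary model carries the same leftover from the two-group design, because it is still worded as a between-group test.

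**Working it through.** **1. Does the stated power apply to the current design?**
The Sample section separates dog group status (a fixed effect) from time (the within-subject effect), so group status cannot mean before versus after pairing. The analysis text defines it as service dog versus control. With one group, the numerator degrees of freedom are 1 − 1 = 0, so the test and its power are undefined. The interactions of group status with covariates involve the same missing factor.

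**2. Can the figure of about 100% be reproduced?**
Not uniquely, because group sizes, units and residual SD are not stated. Assuming two equal groups, 5% alpha and a total N of 130 to 220:

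- 5.54 as a standardised effect: power 1.000.
- Effect SD 0.47 with residual SD 1, averaged over 5 measures with autocorrelation 0.80: above 0.999.
- Standardised difference 0.47: 0.76 to 0.94.
- Difference 0.47 with SD 5.54: 0.07 to 0.09.

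Some readings return the stated figure and others do not. All need two groups.

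**3. Does the second statement fill the gap?**
For 65 per group, the difference detectable with 80% power is (1.96 + 0.8416) × √(2/65) = 0.49 SD. This too is a two-group figure. The paragraph is the closest the documents come to power for PCL, but it names a different outcome and gives no PCL mean, SD or change.

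**4. Completers.**

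- 220 × 0.15 = 33 and 220 − 33 = 187, which is 13 short of 200.
- 200 of 220 would mean a loss of 1 − 200/220 = 9.1%.
- Effect on any detectable difference: √(200/187) = 1.034, about 3%.

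**5. Scale of the missing figure (illustration only).**
Assumptions: two-sided 5%, 80% power, equal variances, complete data, n = 187. In SD units, the detectable baseline-to-final change is (1.96 + 0.8416) × √(2(1 − r)) / √187, where r is the baseline-to-final correlation. The documents do not say over what interval 0.80 applies.

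| Reading of 0.80 | r | Detectable change |
|---|---|---|
| Directly between baseline and final | 0.80 | 0.13 SD |
| Per assessment, 5 measures | 0.8⁴ = 0.41 | 0.22 SD |
| Per assessment, 7 measures | 0.8⁶ = 0.26 | 0.25 SD |
| Per 3 months, to 24 months | 0.8⁸ = 0.17 | 0.26 SD |

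A linear-trend model on the scheduled visits, with 0.80 per 3 months, also gives 0.26 SD at 24 months. The documents give no PCL SD. For an assumed SD of 10 to 15 points the range is about 1.3 points (0.13 × 10) to 4.0 points (0.264 × 15). None of this is the planned mixed model with baseline PCL as a covariate, and it ignores the repeated pre-pairing assessments and missing data.

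**The case against.** **Controls may already be enrolled.** The elimination applies going forward, and the documents do not say whether anyone had joined the control group before. A reader might infer that no control data exist, but the text does not support that. The point therefore rests on the planned enrolment, and the fix is conditional. Even with earlier controls, the Sample section gives no group sizes from which the stated power could follow.

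**The study is probably large enough.** A reader might infer from the obsolete power text that the trial is underpowered. The documents do not show this, and the illustration at 187 completers gives no sign of it. A reader might also take 65 as the realistic number, which would make the detectable change √(187/65) = 1.70 times larger. But 65 is a per-group minimum from the two-group plan, and nothing says it is the number expected to complete.

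**Recalculating may change nothing.** Enrolment was stopped a second time and the study continues with Veterans already consented, so a new figure may not alter the sample size. That stands. It limits the consequence but does not make the stated figure correct.

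**Not all between-group text is obsolete.** This also stands. The sub-analysis of high versus low baseline scorers lies within the service-dog group, and the exploratory aim compares it with a separate pet-dog study. Neither needs the eliminated controls.

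**Conclusion.** The point holds as a mismatch between the design and its power statements; only the completer figure is an arithmetic slip. The power of about 100% belongs to a factor with one level under the planned enrolment, the 65-per-group statement does not replace it, and the primary within-group PCL change has no stated power or detectable difference. The between-group wording of the Hypothesis 1A model is part of the same mismatch.

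The effect on sensitivity cannot be sized from the documents, because the PCL SD, the target change and the actual n are not given. The range of 0.13 to 0.26 SD assumes 187 completers with complete data and shows scale only. The completer slip (187 against 200) is certain on the plan's own inputs but moves a detectable difference by only about 3%.

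**What to change.** 1. State whether any controls were enrolled before the change and whether they will be used.
   - *If not:* remove the group-status power and interaction statements from the Sample section and the 65-per-group statement from the power paragraph. Reword the Hypothesis 1A model as within-group change over time, together with the matching across-group baseline comparisons and the wording that sets the service-dog group against others. Remove the dog-versus-control analyses from the Hypothesis 1B text and the exploratory analysis after it. Keep the high-versus-low baseline sub-analysis and the comparison with the pet-dog study.
   - *If so:* give their number and restate the power with the actual group sizes.
2. State the power or detectable PCL change for the within-group repeated-measures model, with the time point, the PCL SD, the correlation (per assessment or per 3 months) and the n. The illustrative figures above should not be copied into the protocol.
3. Correct the completer figure to 187 if 220 enrolled and 15% loss still apply. Otherwise base it on the number actually consented and expected to be paired and to complete, given the Timeline footnote and the 48-month withdrawal rule.

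The cost is rewording and one recalculation from counts that the sponsor should hold. No enrolment, visit or data collection is added. The downside is that the stated power and completer figures may look less favourable.

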#### *Inclusion/Exclusion Criteria*

Inclusion Criteria	Description
Age	Age greater than or equal to 18 years
Referral	Referral from VA provider which documents PTSD diagnosis.
PTSD	PTSD symptoms as documented in the clinician referral letter.
Treatment for PTSD	In active treatment for PTSD for at least three months at time of enrollment and remain in treatment throughout the duration of the study. Participation will be verified quarterly to ensure that the veteran is still in treatment.
Acceptance by the dog vendor	Will be a function of the vendors that agree to provide dogs.
Dog care	Ability to adequately care for a dog, physically/financially. Has suitable home environment to provide for a dog. Has someone to care for a dog in the absence of the Veteran.
Travel to vendor	Willing and able to travel to vendor location by air or car for pairing
Geographic location	Living the state of Florida

Exclusion Criteria	Description
Mental Health Hospitalization	Veterans will be excluded if they have been hospitalized for mental health reasons in the prior 6 months.
Residence	Not living at the same residence for 6 months. It will be emphasized to the subjects to try and maintain the same residency throughout the duration of the study. Rationale is to ensure access they have appropriate follow up available to them both clinically and for the service dog.
Specific Diagnoses/conditions	Psychoses, Delusions, dementia, active alcohol/substance abuse or dependence, moderate to severe TBI as documented by chart review, suicide flag in CPRS. Study staff identifies a social, mental, or physical condition that prevents the Veteran from giving informed consent or participating in the study

Active suicide /homicide	At time of entry – Active suicide/homicide plan or intent, cognitive disabilities that would preclude safety of animal and ability needed for participation in the study
Children under 10	Veterans with children under 10 years of age in the home for more than 8 hours per day one day a week or more will be unable to participate.
Dual Enrollment without approval	While in this research study participants are required to check with the study team prior to enrolling in a secondary study. Taking part in other research studies may invalidate the results of this research, as well as that of the other research. As a result, participation in this study may be terminated.

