*Intervention:* The vendor(s) will provide SDs for the Veterans enrolled in the study. The dogs will be trained according to their standards and will meet the criteria outlined in the Statement of Work (SOW). All dogs will be trained in basic obedience and a standard set of commands related to mitigation of PTSD symptoms. Due to previous vendor issues, the updated SOW calls for vendors to use only purpose bred dogs (no rescues) which have passed a thorough medical work up and have been “proofed” by a VA dog trainer with extensive experience in training dogs. Veterans will be expected to follow all directions from the vendor(s). Should a Veteran need hospitalization for mental health reasons at any time after they are enrolled, they will not be dropped from the study. Veterans must remain in active treatment for PTSD for the duration of the study. Any Veteran who stops receiving treatment for their PTSD symptoms will be dropped from the study and the service dog removed and returned to the vendor. To ensure Veterans are still in treatment, quarterly verification of mental health treatment will be done by contacting the Veteran’s clinician directly or reviewing the medical record..

Once a Veteran has completed their participation in the study, they may choose to keep their dog or return it to the vendor. If the Veteran chooses to keep their dog at the end of their study participation, they take full responsibility for the care of the dog. Neither the study nor the VA provides further support to the Veteran to care for the dog upon completion of the two year period. If keeping their dog, Veterans may be required to return the dog’s service vest to the vendor who provided it. Once out of the study, the Veteran will be able to contact the vendor directly and receive any follow up services provided by the vendor. Such services may include training support, supplies, support groups, or other services.

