*Alcohol Use Disorder Identification Test (AUDIT-C) and/or Addiction Severity Index –Alcohol Use Disorders Identification Test (AUDIT)-C is a 3-item paper and pencil alcohol screen to identify hazardous drinking or those with problematic alcohol consumption use (abuse and dependence). There is a five-point scale ranging from 0 to 4. The items are summed to obtain a total score ranging from 0-12. For men, a score of 4 or more is considered positive. For women, a score of 3 or more is considered positive. Internal consistency reliability has been reported as 0.80.*

Physical factors: Physical factors will include items that can be drawn from the medical record (co-morbidities, medications). Abstracting medical record data at least one year prior allows for an evaluation of trends or sudden departures from normal care or medication profiles. *In addition, we will track the number of visits and type of therapies that the subjects will be participating in while in treatment for their PTSD.*

*Pittsburgh Sleep Quality Index (PSQI) is a 24 item self-administered survey used to assess sleep-related problems during the past month. The first 19 items are completed by the subject and there are five items completed by a bed partner or roommate. The five items answered by a bed partner or roommate are used as clinical information and are not included in scoring. The first 19 items are grouped into seven components (sleep quality, sleep latency, sleep duration, habitual sleep efficiency, sleep disturbances, use of sleep medication, and daytime dysfunction) each weighted equally on a 0-3 scale. The seven component scores are then summed to yield a global score, which has a range of 0-21; higher scores indicate worse sleep quality. The seven component scores of the PSQI had an overall reliability coefficient (Cronbach's  $\alpha$ ) of 0.83. We will also be using the PSQI-A, addendum for PTSD. The PSQI-A asks an additional ten questions that target PTSD-related sleep problems.*

Psychosocial factors:

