Power analysis for Hypotheses 1: All power analyses were completed with PASS 6.0^81. Given a minimum sample size of 65 (per group), and an alpha of 0.05, we have over 80 percent power to detect differences in socioeconomic characteristics. This power analysis is based on changes in mean and SD (PCL-C) from prior published studies. This power analysis allows for the addition of three covariates to be added to the model.

***Hypothesis 2A:*** *Individuals partnered with SDs will have decreased mental health care utilization, over time.* We expect the SD group to experience diminished healthcare utilization over time. A within subject repeated measures will be completed to determine changes over time for healthcare utilization.

***Hypothesis 2B:*** *Individuals partnered with SDs will have decreased overall health care utilization, over time.* We expect the SD group to experience diminished healthcare utilization over time. A within subject repeated measures will be completed to determine changes over time for healthcare utilization.

*Exploratory Aim:* We will compare our findings to data collected in similar study entitled, “A Study of Dog Adoption in Veterans with Posttraumatic Stress Disorder” which is being conducted by [name] at the South Texas Veterans Healthcare System in San Antonio, TX. This is a 2-year pilot study examining the use of shelter dog adoption as a supplement to standard care in reducing PTSD symptoms in Veterans. 24 veterans will be randomized to adopt a dog from the Humane Society while another 24 (control group) will be randomized to a wait-list and be eligible to adopt a dog after 3 months. Outcome measures will be assessed at baseline and at 3 intervals (1, 3, and 6 months post-randomization) for Veterans in the experimental group and 4 intervals (1, 3, 4, and 6 months) for those in the control group. Data collection will be in the form of face-to-face interview as well as self administered paper forms. CPRS records will be reviewed for changes in mental health treatments, medications, diagnoses, and other health related variables. Analysis will be completed which will examine similar measures (e.g. PCL checklist, depression, community integration) across our Veterans who received service dogs at three time points (baseline, three and six months) to their Veterans who received dogs as pets. As this is an exploratory analysis, power analysis was not completed.

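### Hypotheses 2A/2B name no reference assessment; if it is enrolment, the entry rules partly set that level, and the waiting-period data that would avoid this go unused

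*Combined protocol and SAP*

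**What the plan says.** All references are to the combined protocol and SAP.

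- **Entry.** The Inclusion/Exclusion Criteria state that "Veterans will be excluded if they have been hospitalized for mental health reasons in the prior 6 months". They also require each Veteran to be "In active treatment for PTSD for at least three months at time of enrollment and remain in treatment throughout the duration of the study".
- **After entry.** Under Intervention: "Should a Veteran need hospitalization for mental health reasons at any time after they are enrolled, they will not be dropped from the study". The same paragraph adds: "Any Veteran who stops receiving treatment for their PTSD symptoms will be dropped from the study".
- **Timing.** Specific Aims counts the assessments from enrolment, and the Screening Visit paragraph has the baseline questionnaires completed once eligibility is confirmed. Design and the recruitment section then repeat the assessment every 3 months until a dog is available (every 6 months once 24 months have passed).
- **Comparator.** Design reports, of the "control (no dog) group, this group has been eliminated going forward with the study".
- **Measure.** Table 2 defines utilization as a number of visits over the preceding 3 months, for mental health and for general care. The Healthcare utilization paragraph asks instead about visits over the past year, averaged per month. Neither says whether an inpatient admission counts.
- **Analysis.** For both 2A and 2B the whole method is: "A within subject repeated measures will be completed to determine changes over time for healthcare utilization".
- **Records.** Under Physical factors: "Abstracting medical record data at least one year prior allows for an evaluation of trends or sudden departures from normal care". This is not linked to 2A or 2B.

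**The concern.** Without a comparator, the conclusion for Aim 2 rests entirely on the level from which change is measured. The 2A/2B paragraphs do not say which assessment supplies that level. If it is the one at enrolment, eligibility partly fixes it: recent mental health admission is barred before entry and permitted afterwards. Inpatient mental health use would then tend to rise from the reference whatever the dogs do, and a real reduction could be hidden. The protocol already collects data free of this restriction (the repeated waiting-period assessments), but the 2A/2B analysis does not use them.

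**Working it through.** The protocol gives no admission rate, visit rate or power for 2A/2B, so there is no planned figure to reproduce. The rates below are assumptions, shown as ranges, and every result assumes no dog effect.

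**Inputs**
- From the protocol: up to 220 enrolled with 15% dropout (33), so 220 − 33 = 187. (The same paragraph expects 200 completers; 200 would change the counts below only slightly.)
- From the protocol: 6-month exclusion window before entry; look-back of 3 months (Table 2) or 12 months (Healthcare utilization paragraph).
- Assumed: 0.05, 0.10 or 0.20 mental health admissions per Veteran-year.

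**1. Three-month look-back at enrolment.** The 3 months lie wholly inside the 6-month exclusion window. If admissions count, the enrolment value is 0 for every Veteran. The expected number in a later 3-month window is 187 × 0.25 × rate:
- 0.05: 2.3
- 0.10: 4.7
- 0.20: 9.4

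Like for like, this is 0 against about 2 to 9. If the dogs halved the rate, the comparison would still be 0 against about 1.2 to 4.7, an apparent rise.

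**2. Could this reach significance?** As an illustration, take each Veteran's any-admission status at enrolment (always no) and in one later 3-month window, and apply an exact two-sided McNemar test. With all discordant pairs in one direction, p = 2 × 0.5^d. This gives 0.0625 for d = 5 and 0.031 for d = 6, so six are needed. Let rates vary between Veterans as a gamma distribution with mean m and shape k. Given no admission in the prior 0.5 year, the chance of at least one in the next 0.25 year is

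p = 1 − [(k/m + 0.5)/(k/m + 0.75)]^k.

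For m = 0.20 and k = 1, p = 1 − 5.5/5.75 = 0.0435. The chance of a significant false rise is P(X ≥ 6) with X ~ Binomial(187, p). From k = 0.25 up to no variation between Veterans:
- 0.05 per year: 0.02 to 0.03
- 0.10 per year: 0.17 to 0.32
- 0.20 per year: 0.58 to 0.90

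The effect is negligible at the low rate and serious at the high one.

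**3. Past-year look-back at enrolment.** Here 12 − 6 = 6 months are unrestricted. At m = 0.20 and k = 1 the post-entry rate is k/(k/m + 0.5) = 1/5.5 = 0.182 per year. That gives 9.1 admissions per 100 Veterans at enrolment against 18.2 per 100 in a 12-month follow-up window. The shortfall is half, not total.

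**4. Moving the reference later (same rate and shape).**
- 3-month look-back taken at least 3 months after consent: 4.55 per 100, equal to 4.55 per 100 in follow-up. The artefact is gone.
- 12-month look-back: still 9.1 per 100 after a wait of 3 or 6 months; 18.2, equal to follow-up, only after 12 months.

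The exclusion covers time before entry, so person-time after consent counted from dated records is clear of it from the first day.

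**5. Outpatient visits.** Treatment is required at entry and throughout. If each Veteran's underlying rate is constant and at least one visit is required in both quarters, the two quarters are interchangeable and their means must agree. A simulation with mean 2 visits per quarter and shape 1 gives 3.33 and 3.33. The continuing-treatment rule therefore produces no drift among those retained. Comparing retained Veterans' follow-up with everyone's baseline gives an apparent rise of 2% to 15% (means of 2 to 8 visits per quarter).

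**The case against.** The strongest reply is that admissions are not shown to be part of the endpoint. Both definitions speak of visits, so a zero baseline for admissions may concern something that is never analysed. This stands as a condition. The protocol does not exclude admissions either, and Aim 2 is framed around the costs of total and mental health care utilization, so the plan needs to say.

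Second, the enrolment assessment may not be the reference. The protocol applies the word baseline to the whole pre-pairing series, and waits of up to 48 months are allowed. This also stands: the defect is an unnamed reference and unused data, not a proven wrong choice.

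Third, admissions would be a small part of a pooled count. At an assumed 2 to 8 visits per quarter, 187 Veterans make 374 to 1,496 visits, so 2.3 to 9.4 admissions are about 0.2% (2.3/1,496) to 2.5% (9.4/374) of that number. The bias therefore matters mainly where admissions are analysed separately or costed.

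A reader might go further and infer three things that the documents do not support:
- **That the entry rules produce a false decrease.** The admission rule pushes the other way.
- **That outpatient visits must fall as courses of therapy end.** Intensity may change over time, but no visit rates are given, three months of treatment is only a minimum, and treatment continues throughout.
- **That the reference should begin some months after consent to escape the exclusion window.** That window ends at entry.

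**Conclusion.** The concern holds in a limited form. Hypotheses 2A and 2B are uncontrolled within-subject comparisons with no named reference assessment, and they leave the pre-pairing series unused. If enrolment is the reference, admissions count and the look-back is 3 months, the reference contains no mental health admissions by rule, against about 2 to 9 per 3 months later in 187 Veterans at an assumed 0.05 to 0.20 per Veteran-year. With the past-year look-back, half the window is affected. The bias is toward an apparent rise: it works against the hypothesised decrease and can mask a real one. For 2B it acts directly only on the mental health share of total use.

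It would be tempting to set the enrolment zero against all admissions over 24 months of follow-up, but those windows are unequal and the contrast should not be used. Any change in outpatient visits without a dog effect is possible, but its size and direction cannot be fixed from the documents.

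**What to change.** In the Hypothesis 2A and 2B paragraphs:

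1. State that the enrolment look-back is not the reference. Compare the utilization rate in the waiting period between consent and pairing with the rate after pairing. Use person-time from dated records, or only those assessments whose look-back starts after consent.
2. Include the pre-pairing time trend, for example in a segmented count model: a negative binomial mixed model with log person-time as offset, and terms for time since consent, a step at pairing, and change in slope after pairing.
3. State whether admissions count, and analyse mental health visits and mental health admissions separately.
4. Reconcile the 3-month and past-year look-backs. A past-year question asked 3 months after pairing reaches 12 − 3 = 9 months back into the time before pairing, so it also blurs the contrast itself.
5. Use the year of records before consent as a descriptive check on trend, not as the reference.

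No eligibility or retention rule needs to change. The cost is analysis wording, since the waiting-period assessments and record abstraction are already planned; dated visits and admissions would have to be among the items abstracted. The downside is that Veterans paired soon after consent contribute little or no pre-pairing time. Without a comparator, some natural change over time will also remain unseparated from the dog effect, and the report should say so.
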